MGH – Massachusetts General Hospital

PA - Pulmonary Artery

PI – Principal Investigator

RIJ – Right Internal Jugular

RVAD – Right Ventricular Assist Device

RVF – Right Ventricular Failure

SAE – Serious Adverse Event

sCr – Serum Creatinine

VIS – Vasoactive Inotrope Score

II. BACKGROUND AND SIGNIFICANCE

Prior studies have shown that left ventricular assist device (LVAD) implantation commonly results in right ventricular failure (RVF) due to changes in septal positioning and the left heart cardiac output returning to normal, causing acute right ventricular overload. Right ventricular dysfunction and failure after LVAD implantation is known to increase morbidity and mortality and contribute to longer post-implant hospital length of stay. More severe right ventricular failure is highly correlated with poor prognosis and death post-LVAD implantation (Kang).

In current practice, patients who receive LVADs require right heart support, provided in the form of inotropes. Additionally, the operational speed of the newly implanted LVAD is typically purposely low for the first 24 – 48 hours to reduce the negative impact on RV geometry and function. Vasoactive inotrope score (VIS) is a measure that quantifies the amount of right heart support required post-operatively, including dopamine, dobutamine, milrinone, epinephrine, norepinephrine, and vasopressin. It has been used in other studies as a surrogate marker for hemodynamic cardiovascular derangement (Han). The use of 2 or more inotropic agents has been found to be correlated with a higher right atrial to pulmonary capillary wedge pressure ratio and a lower pulmonary artery pulsatility index when compared with 0-1 agents. This means that a higher VIS is correlated with right heart dysfunction (Morine). The use of two or more vasopressors or inotropes is also correlated with worsening of biomarkers such as higher creatinine, alanine aminotransferase (ALT), and aspartate aminotransferase (AST) (Morine). Therefore, greater use of vasopressors and inotropes could be associated with end organ dysfunction. Higher VIS is also associated with increased hospital mortality (Na).

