The primary analysis will be performed in an intention-to-treat fashion using a two-sided T-test (alpha level=0.05). The null hypothesis is that the mean maximal 24-hour VIS will not differ between intervention and historical groups. The alternate hypothesis is that compared to standard of care (historical cohort), placement of an RVAD within 48 hours before or during LVAD implantation will decrease the mean maximal 24-hour VIS score by 50%. Analysis assumptions will include independence of study groups and lognormal (or normal) distribution of data in each group.

SECONDARY OUTCOMES

Secondary end points will include:

- Total VIS (throughout hospitalization)
- ICU length of stay (LOS)
- Total post-operative LOS after LVAD implantation
- Survival at discharge after LVAD placement
- Survival at 1 year after LVAD placement or heart transplant
- End organ dysfunction including
 - o Development of acute kidney injury (AKI) – defined as increase in serum creatinine (sCr) to 4mg/dl or greater, a 150% or greater increase in sCr over the baseline preoperative value, or a new requirement for renal replacement therapy
 - o Liver dysfunction
- LVAD device speed

Cox proportional hazard models (one sided, 0.05 significance level) will be used to compare rates of secondary outcomes between intervention and historical arms. Event rates and relative risks will also be estimated for each of these outcomes.

POWER ANALYSIS

Sample size calculations are estimated based on expected effect size, which was determined based on expert consensus (reduction in the mean maximal 24-hour VIS score by 50% in the intervention arm compared to the historical controls). 80% power will be generated with 2-tailed confidence interval of 0.05 from a sample size of 34 patients (17 per group). Estimating a

standard deviation of 0.5 of the outcome in the population and 20% attrition and/or cross-over, investigators anticipate that 20 patients will be needed to test this hypothesis. This power estimation assumes a lognormal distribution of the data. We plan to allow for 25 patients to participate in the prospective arm of the study to allow for incorrect assumptions.

IX. RISKS AND DISCOMFORTS

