Previous studies have shown that RVAD placement post-LVAD implantation improved hemodynamics, including an increase in cardiac index and decrease in central venous pressure. These patients also experienced reversal of shock, favorable survival, and improved LVAD flow. RVADs also mitigate the need for inotropes, and thereby lessen inotrope-related adverse outcomes such as worsening biomarkers of end organ function. We hypothesize that preemptive RVAD placement could lead to a lower vasoactive inotrope score, better clinical outcomes, shortened hospital length of stay, and improved end-organ function in patients with LVADs. Therefore, subjects may receive direct benefits from their participation in this study. This study may also benefit future LVAD patients by potentially improving standard of care procedures surrounding LVAD management.

XI. MONITORING AND QUALITY ASSURANCE

During the course of the trial, the PI will oversee the conduct of the trial and will review study documents for completeness and accuracy as well as compliance with the study protocol and applicable regulations. The PI is ultimately responsible for protecting the safety and welfare of all subjects.

The PI is responsible for reviewing all laboratory, imaging and procedural reports for clinical significance. It is the PI's responsibility to determine if any reports are significant or meet the guidelines for adverse event and/or serious adverse event reporting for both the sponsor and the IRB.

Safety data will be continuously monitored and reviewed in order to quickly identify any unforeseen risks to subjects. The physician investigator will perform regular, internal reviews of all adverse events. Events will be reported to the IRB per the outlined requirements and a summary of the safety data will be sent the IRB at the time of the annual renewal. Unanticipated problems involving risks to subjects or others including adverse events will be reported to the PHRC in accordance with PHRC unanticipated problems reporting guidelines.

All serious adverse events (SAEs) will be assessed by the principal investigator, documented and reported to the IRB according to PHRC guidelines. AEs that are not serious but that are notable and could involve risks to subjects will be summarized in narrative or other format and submitted to the IRB at the time of continuing review.

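### One-sided Cox models are the stated comparison for survival at discharge and both length-of-stay outcomes, where death and live discharge compete; the hazard ratios do not measure what these endpoints name

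*Protocol*

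**What the plan says.** Protocol section VIII, Secondary Outcomes, lists among others ICU length of stay, "Total post-operative LOS after LVAD implantation", "Survival at discharge after LVAD placement" and survival at 1 year. One method is then fixed for the whole list: "Cox proportional hazard models (one sided, 0.05 significance level) will be used to compare rates of secondary outcomes between intervention and historical arms". No outcome is exempted. The next sentence adds: "Event rates and relative risks will also be estimated for each of these outcomes".

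The section does not define the event or the censoring for these outcomes, and it names no favourable direction for the one-sided test.

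Two other sections bear on the point. Background and Significance says that right ventricular failure after LVAD implantation "is known to increase morbidity and mortality and contribute to longer post-implant hospital length of stay". Potential Benefits gives "shortened hospital length of stay" as one of the hypothesised effects of the device.

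**The concern.** A patient's stay ends in one of two ways, live discharge or death, and each prevents the other. The protocol expects the intervention to shorten stays and describes a condition that affects both mortality and stay, so the two hazards may well move by different amounts.

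- **Survival at discharge** is a yes/no status. The usual way to put it in a Cox model is time to in-hospital death, censored at live discharge. That estimates the death rate per day among those still in hospital. If survivors leave sooner, fewer patients remain at risk and the daily rate rises, even when the same proportion die.
- **ICU and post-operative stay.** If death counts as the end of the stay, an early death is scored as a short stay. If death is censored, the model treats that patient as someone who would have gone home at the same rate as the others.

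The risk is that equal survival is reported with a hazard ratio suggesting harm, or that extra deaths are reported as a shorter stay.

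**Working it through.** The protocol gives no figure for these outcomes, so there is none to reproduce. From the protocol come the Cox prescription and the arm sizes, 25 v 25 (Study Procedures). Every mortality risk and stay below is an assumption.

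**1. Survival at discharge, constant hazards.** Let *a* be the daily hazard of live discharge and *d* that of death.
- In-hospital death risk = d/(a+d).
- Cox hazard ratio for death, discharge censored = d1/d0.

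Assume control a = 1/20 = 0.05 and a death risk of 15%, so d = 0.05 × 0.15/0.85 = 0.00882.

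| Assumed change in intervention arm | Death HR | In-hospital death, control v intervention | Relative risk |
|---|---|---|---|
| d × 1.3, a × 2.0 | 1.3 | 15.0% v 0.01147/0.11147 = 10.3% | 0.69 |
| d × 0.8, a × 0.6 | 0.8 | 15.0% v 0.00706/0.03706 = 19.0% | 1.27 |

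In both rows the hazard ratio and the relative risk lie on opposite sides of 1. Cox fits to 4,000 simulated patients per arm agree: HR 1.27 while deaths fell from 15.0% to 9.9%, and HR 0.79 while deaths rose from 15.6% to 19.5%. Over control risks of 5% to 20% the relative risks are 0.66 to 0.70 and 1.25 to 1.31, so the reversals persist.

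**2. Survival at discharge, equal mortality.** Assume 16% die in both arms, with exponential times: mean 10 days to death, mean 20 days to discharge for control survivors. Large-sample Cox hazard ratios for death are:
- survivors' mean stay cut to 15 days: 1.14 to 1.17 across repeated calculations;
- survivors' mean stay cut to 10 days: 1.50 to 1.54.

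The true relative risk is 1.0 in both.

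**3. Length of stay.** With death counted as the end of stay, HR = (a1+d1)/(a0+d0). Keep a = 0.05, control risk 15%, and triple the death hazard (d1 = 0.02647):
- HR = 0.07647/0.05882 = 1.30;
- mean stay 1/0.05882 = 17.0 v 1/0.07647 = 13.1 days;
- in-hospital death 15% v 0.02647/0.07647 = 35%.

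This reads as a shorter stay although discharge is no faster. Over control risks of 5% to 20% the HR is 1.10 to 1.40. With deaths censored, HR = a1/a0 = 1.0, and the lost live discharges are not seen.

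A second set of assumptions takes mortality of 8% v 24%, deaths at a mean of 5 days, and identical survivor stays with mean 20 days. Median stay solves 0.92·exp(−t/20) + 0.08·exp(−t/5) = 0.5 for control, giving 12.5 days. With 0.76 and 0.24 as weights it is 9.8 days. The end-of-stay HR is 1.12 to 1.15 across calculations. With deaths censored the discharge HR is 0.95, so a threefold mortality is barely visible.

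**4. At 25 per arm** (one-sided 5% score test, 4,000 replicates, inputs of steps 2 and 3). A 16% risk is 0.16 × 25 = 4 deaths per arm.
- Death, equal mortality: a significant result towards harm in 7% of trials (stay cut to 15 days) or 16% (cut to 10 days), against 5% with no change. If the test is aimed at benefit, false benefit falls to 3% and to between 1% and 2%.
- Stay with 8% v 24% mortality: a significant shorter stay in 13% of trials, against about 5% with no difference.

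**The case against.** **Censoring rules belong in a SAP.** The protocol nowhere says that patients are censored at live discharge, and a reader might infer that it prescribes this or that its silence on competing risks is the fault. Neither follows: such rules are commonly left to a SAP, which may exist. What stands is that the protocol itself names the Cox model as the comparison, and for these three outcomes each usual coding has the defect shown.

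**Relative risks are promised too.** This largely stands for survival at discharge: 84% v 84% would be printed beside any hazard ratio. But Cox is the named comparison, with no rule for which prevails if they differ. A relative risk does not summarise a duration.

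**The effect is modest here.** This stands. Few deaths mean little distortion of stay: at 5% control risk even a tripled death hazard gives only 1.10. A reader might infer that the distortion would change the trial's message. That is not shown: these are secondary outcomes, the primary is VIS, and in the 8% v 24% case about 2 v 6 deaths would be visible in the survival rates.

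**Larger ratios can be produced.** Halving all in-hospital times gives 2.0 under constant hazards but about 1.5 under the exponential mixture of step 2. In that scenario deaths also occur sooner, so the figure should not be relied on.

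**Cause-specific Cox for time to live discharge is an established analysis.** It is valid as a discharge rate among those still in hospital. It does not answer how long patients stay or how many go home.

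**Conclusion.** The point holds as a poor fit between a stated method and three named endpoints. The Cox hazard ratio for in-hospital death does not measure survival to discharge: under the assumed inputs it is about 1.2 to 1.5 with equal mortality, and it can lie on the opposite side of 1 from the relative risk. For stay, the end-of-stay hazard ratio can credit early deaths as shorter stays (about 1.12 to 1.15 with 8% v 24% mortality), and censoring deaths conceals them.

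Wrong direction is a possibility, not a certainty; it needs death and discharge hazards to shift by different amounts. The sizes rest on assumed mortality and stay, and at 25 per arm the rise in error is modest. The two stay outcomes carry most of the weight, because the promised relative risk already partly covers survival at discharge. Survival at 1 year is not affected in this form. The change is worth making because it is cheap.

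**What to change.** - **1-year survival:** keep the Cox model.
- **Survival at discharge:** make the relative risk already promised, or a risk difference, with an exact confidence interval the stated comparison.
- **ICU and post-operative stay:** compare the cumulative incidence of live discharge with death as a competing event, or use a rank test in which deaths before discharge rank worst. State which.
- **Direction:** if any one-sided test is retained, name the favourable direction for each outcome. It is below 1 for a death hazard ratio and above 1 for a discharge hazard ratio.

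Both stay options use discharge and death data the study already collects, so the cost is wording in the protocol or SAP. The downside is that stay is no longer summarised by a simple hazard ratio; survivors' stay can still be shown descriptively.

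Days alive and out of hospital or ICU to a fixed day is optional. It needs readmission and ICU-return dates in both cohorts, and the Data Collection Schedule lists no such item, so it should not be assumed to be free of new data.

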(CI), which results in the improvement of systemic and end-organ perfusion, as well as the reversal of cardiogenic shock. Impella RP placement has also been shown to decrease central venous pressure (CVP) (Anderson). This improvement in hemodynamics facilitates the weaning of inotrope and vasopressor support. LVAD flow has also been shown to improve after Impella RP support is initiated (Anderson).

ProtekDuo, manufactured by TandemLife, is another device placed percutaneously for right heart support via the right internal jugular (RIJ) vein. Like the Impella RP, use of the ProtekDuo is associated with improved hemodynamics in patients with right ventricular failure. Studies looking at concomitant insertion of the ProtekDuo and LVAD to preempt RVF in patients with impaired RV function have shown advantageous effects on patient outcomes compared to insertion post-LVAD (Schmack). It is expected that preemptive placement of RVADs prior to or during LVAD implantation to preemptively treat RVF will similarly result in improved patient outcomes.

III. SPECIFIC AIMS

The purpose of this study is to compare clinical outcomes of standard of care treatment versus preemptive percutaneous right ventricular assist device (RVAD) placement surrounding left ventricular assist device (LVAD) implantation. We hypothesize that the use of the RVAD will mitigate need for inotropic support, reducing the vasoactive-inotrope score (VIS) by 50%, and will improve end organ function in patients compared to standard of care.

IV. SUBJECT SELECTION

This trial will include both a prospective interventional cohort and a retrospective control cohort. The prospective interventional cohort will consist of patients undergoing LVAD implantation at Massachusetts General Hospital. These patients will receive an RVAD (either the ProtekDuo or Impella RP) prior to or during LVAD implantation. The historical control cohort will consist of retrospective data collection on patients who have undergone LVAD implantation in the past. This group will be age and sex matched with the enrolled prospective interventional patients.

INCLUSION:

- Ages 18-75
- Accepted for LVAD implantation by MGH multidisciplinary team

EXCLUSION:

- Disorders of the pulmonary artery wall that would preclude placement or correct positioning of RVAD
- Presence of mechanical valves
- Mural thrombosis of the right atrium or vena cava
- Anatomic conditions precluding insertion of the RVAD

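### The stated 17 per group is not a lognormal result: it is the answer for an untransformed difference of 0.5 with SD 0.5, and the 20% inflation of it is 22, not 20

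*Protocol*

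**What the plan says.** The protocol's Power Analysis subsection (section VIII) takes a halving of mean maximal 24-hour VIS as the effect, set by expert consensus, and states: "80% power will be generated with 2-tailed confidence interval of 0.05 from a sample size of 34 patients (17 per group"). It then assumes a "standard deviation of 0.5 of the outcome in the population and 20% attrition and/or cross-over", and concludes that "investigators anticipate that 20 patients will be needed to test this hypothesis". The next sentence reads "This power estimation assumes a lognormal distribution of the data". The last one sets the planned size: "We plan to allow for 25 patients to participate in the prospective arm of the study to allow for incorrect assumptions". Study Procedures (section VI) gives the comparison as 25 prospective subjects against 25 matched retrospective controls.

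The Primary Endpoint subsection fixes the test: "The primary analysis will be performed in an intention-to-treat fashion using a two-sided T-test (alpha level=0.05"). On the distribution it says only: "Analysis assumptions will include independence of study groups and lognormal (or normal) distribution of data in each group". Neither subsection says whether the SD of 0.5 is in VIS points, a fraction of the control mean, or on a log scale, or whether the t-test is run on logged VIS.

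**The concern.** The paragraph supplies inputs, a distributional model and a result. A reader who applies that model to those inputs does not get that result. The natural lognormal calculation takes 0.5 as the SD of log VIS and the effect as a ratio of 0.5, and it gives a much smaller number than 17.

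At stake is the meaning of the margin. The protocol justifies 25 as protection against wrong assumptions, and Monitoring and Quality Assurance (section XI) provides for going back to the IRB if assumptions fail and more patients are needed. An SD without a scale cannot be compared with observed data, so nobody could tell whether that condition had been met. The same paragraph also carries a wrong inflation figure, and it counts cross-over as loss although the stated analysis keeps those patients in.

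**Working it through.** **Inputs (protocol, section VIII).** Two-sided alpha 0.05; 80% power; equal groups; 50% reduction; SD 0.5 with no scale; 20% attrition and/or cross-over. Power is from the noncentral t distribution with noncentrality d / sqrt(1/n1 + 1/n2) and n1 + n2 − 2 degrees of freedom.

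**Step 1: reproduce 17.** Work in units of the control mean, untransformed: difference 0.5, SD 0.5, so d = 0.5/0.5 = 1.0.
- Normal approximation: 2 × (1.960 + 0.842)² / 1.0² = 15.7, so 16.
- Noncentral t: 16 per group gives 78.1%, 17 per group gives 80.7%. The stated 17 is reproduced exactly.

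This needs the same absolute SD in both arms although the mean halves. If the SD were 50% of each arm's own mean, d = 0.5 / sqrt((0.25 + 0.0625)/2) = 1.265 and 11 per group would do.

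**Step 2: apply the stated lognormal model.** With the same log-SD in both arms, halving the mean is a shift of ln 2 = 0.693 on the natural-log scale. With log-SD 0.5, d = 0.693/0.5 = 1.386.
- 9 per group gives 78.8%, 10 per group gives 83.4%, so 10 are needed.
- 17 per group gives 97.5%.

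If 0.5 is instead the coefficient of variation of lognormal data, the log-SD is sqrt(ln 1.25) = 0.472, d = 1.467, and 9 per group suffice.

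**Step 3: what log-SD would give 17?** Exactly 80% at 17 v 17 needs d = 0.991, so a natural-log SD of 0.693/0.991 = 0.70, not 0.5.

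**Step 4: does the scale of the test rescue 17?** By simulation, an untransformed t-test on lognormal data with log-SD 0.5 has 78.0% power at 10 per group, 82.4% at 11 and 95.7% at 17. The mismatch does not depend on logging the data.

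**Step 5: power at the planned size.**

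| Reading of SD 0.5 | d | n per group for 80% | Power, 17 v 17 | Power, 25 v 25 |
|---|---|---|---|---|
| Fraction of control mean, untransformed, equal absolute SDs | 1.000 | 17 | 80.7% | 93.4% |
| Natural-log SD | 1.386 | 10 | 97.5% | 99.8% |

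**Step 6: inflation for loss.** 17/(1 − 0.2) = 21.25, so 22. The stated 20 looks like 17 × 1.2 = 20.4 rounded down. Twenty less 20% leaves 16. Only the prospective arm can lose patients, since "The historical control cohort will consist of retrospective data collection on patients who have undergone LVAD implantation in the past". At d = 1.0, 16 v 20 still has 82.5%.

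**Step 7: cross-over.** Under intention to treat, a patient who crosses over stays in the prospective arm and responds like a control. Simulating 25 v 25 with that many prospective patients at control level:
- 5 of 25 (the whole 20% as cross-over): about 77% at d = 1.0, 96% at d = 1.386.
- 4 of 25: about 81% and 97%.

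**The case against.** The best defence is that no arithmetic is shown to be wrong. The protocol never calls 0.5 a log-SD, 17 follows at once from 0.5/0.5, and 25 v 25 has ample power either way, so this is only a missing label. It is true that 17 is correct for the untransformed calculation and that the design is unaffected. But the paragraph attributes the figure to a lognormal model, and on such a model an SD of 0.5 does not give 17, whether it is a natural-log SD (10) or a coefficient of variation (9). That is a wrong statement, not only an unlabelled one. A statistical analysis plan could fix the scale of the test, but it would not make this paragraph agree with itself.

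Two further readings are tempting, and the document supports neither. One takes 0.5 as a log-variance (log-SD 0.707), which brings 17 and lognormal nearly together: 16.3 by normal approximation, 18 exactly. The text says standard deviation. The other takes 0.5 as a log10 SD (d = 0.602), from which a reader might infer that the trial is underpowered: 45 per group needed, 55.0% at 25 v 25. Nothing in the protocol points to base 10, and this reading is far from reproducing 17.

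The inflation and cross-over points are small, as the defence would say. The next sentence but one names the prospective arm for the 25, and the fall to about 77% needs the entire allowance to be cross-over with complete loss of effect.

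**Conclusion.** The point holds as an internal disagreement between the stated model and the stated sample size, and it should be corrected. Seventeen per group belongs to an untransformed comparison with d = 1.0. On the lognormal model that the paragraph names, with natural-log SD 0.5, the figure is 10 and the power at 17 is 97.5%. The inflated figure should be 22 if 17 is kept; that error is minor.

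It does not follow that the trial is too small. On both readings 25 v 25 is adequate (93.4% or 99.8%), and it keeps 80% power up to a natural-log SD of about 0.86, or an SD of about 0.62 of the control mean. Only full 20% cross-over at d = 1.0 takes it slightly below 80%. These figures assume a common SD in both arms on the scale used and a true halving of the mean.

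**What to change.** Rewrite the Power Analysis paragraph on the one scale on which the t-test will be run, using whichever of these is meant:

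- **Log scale:** ratio of 0.5 in maximal 24-hour VIS, natural-log SD 0.5, t-test on log VIS; 10 per group for 80% power (13 after 20% loss, from 10/0.8 = 12.5); 25 v 25 gives 99.8%.
- **Untransformed scale:** difference and SD each 50% of the control mean, same absolute SD in both arms; 17 per group for 80% power (22 after 20% loss); 25 v 25 gives 93.4%. Delete the lognormal sentence here, and align the distributional assumption in the Primary Endpoint subsection, which now allows either form; otherwise the mismatch only moves.

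Label the inflated figure as the prospective arm. State attrition and cross-over separately, with cross-over as dilution under intention to treat and the resulting power at 25 v 25.

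The cost is one paragraph and one aligned sentence, with no added patients, visits or procedures. If the sponsor wants to check the SD before enrolment ends, it would have to come from available past LVAD patients: the controls are matched to enrolled subjects, so the matched set is complete only after enrolment.

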All LVAD candidates at Massachusetts General Hospital (MGH) will be screened for trial eligibility. Every eligible candidate will be asked to participate. Subjects who consent to the study will undergo pre-operative or intra-operative placement of an RVAD, which will be left in up to 72 hours postoperatively. If it is determined that a subject requires support for longer than 72 hours, the treating physician will consider utilizing a more durable form of right ventricular support (CentriMag paracorporeal RVAD requiring direct cannulation), as is standard practice. The type of RVAD (Impella RP or ProtekDuo) inserted will be determined by patient needs and venous access and will be up to the discretion of the treating physician. The use of the ProtekDuo will be prioritized due to the benefit of the jugular approach in device placement, which does not limit patient mobility. If there is no jugular access, the Impella RP, which is placed through a femoral approach, will be used. We aim to enroll 25 subjects in the prospective interventional cohort, and compare to 25 subjects in the matched retrospective control cohort.

All enrolled patients in the prospective interventional cohort will undergo surgical placement of a percutaneous RVAD within 48 hours preoperatively to LVAD implantation, at the time of LVAD implant, or immediately following the implant. After removal of the RVAD, subjects will receive standard treatment according to MGH's standard of care. Data will be obtained for subjects in both cohorts from the electronic medical record in EPIC at MGH and will be reviewed throughout the study through the 1-year follow-up period. Other standard of care tests are administered regularly at LVAD follow-up visits, including: the KCCQ-12 and EQ-5D surveys, a neurocognitive trailmaking test, and a six-minute walk and gait speed test. These are collected per standard of care at the following timepoints: pre-implant, 3 month (+/- 30 days), 6 month (+/- 60 days), and 1 year (+/- 60 days). These results will also be collected and entered to the study database.

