We will perform an interim safety/outcomes analysis after the first 10 subjects have been enrolled to ensure that the anticipated risk/benefit assessment remains unchanged. The report will be made available to the IRB in a timely manner. If this analysis shows that 10 subjects provide enough data to draw significant conclusions, enrollment will be stopped and the study will be concluded. If other assumptions prove to be wrong and additional patients will be needed, this will be carefully considered and communicated to the IRB prior to proceeding.

XII. REFERENCES

5. Na, S. J., Chung, C. R., et. Al. (2018). Vasoactive Inotropic Score As A Predictor Of Mortality In Adult Patients With Cardiogenic Shock. *Journal of the American College of Cardiology*, 71(11). doi: 10.1016/s0735-1097(18)31355-x

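### The 10-subject interim look can conclude the study on undefined significance, while the primary analysis is stated and sized as a single 5% test

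*Protocol*

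**What the plan says.** Protocol section XI (Monitoring and Quality Assurance), last paragraph: "We will perform an interim safety/outcomes analysis after the first 10 subjects have been enrolled". Its stated purpose is "to ensure that the anticipated risk/benefit assessment remains unchanged". The same paragraph then gives the look a second function: "If this analysis shows that 10 subjects provide enough data to draw significant conclusions, enrollment will be stopped and the study will be concluded". It also allows for more patients if other assumptions prove wrong, after communication with the IRB.

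Protocol section VIII, Primary Endpoint, defines the primary analysis "using a two-sided T-test (alpha level=0.05") and its hypothesis: "The null hypothesis is that the mean maximal 24-hour VIS will not differ between intervention and historical groups". Under Power Analysis, 80% power at that level comes "from a sample size of 34 patients (17 per group"), with a "standard deviation of 0.5 of the outcome in the population and 20% attrition and/or cross-over". Section VI sets the final size: "We aim to enroll 25 subjects in the prospective interventional cohort, and compare to 25 subjects in the matched retrospective control cohort".

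Neither section VIII nor section XI mentions an interim boundary, a split of the 0.05, or an adjusted final level.

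**The concern.** The look has a safety purpose, but its consequence is triggered by significance. The study can end and be concluded on outcomes, with no stated outcome, test or threshold for that decision.

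Three things are at stake:

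- **Error rate.** If the look tests the primary outcome, the null hypothesis can be rejected at 10 subjects or at 25. The stated 5% covers only one of those tests.
- **Size of effect.** A study that stops because an early difference is large enough to be significant tends to overstate that difference.
- **Information lost.** A stop at any level leaves 10 treated patients rather than 25 for the secondary outcomes and for the device complications listed in section IX.

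**Working it through.** **Inputs from the protocol.** Two-sided t-test at 0.05 on mean maximal 24-hour VIS; 80% power; 17 per group; SD 0.5; 50% reduction; lognormal data (section VIII). Final comparison 25 v 25 (section VI). Look after 10 enrolled (section XI).

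**Assumptions.** The look tests maximal 24-hour VIS. Its level is not stated, so 0.05, the only level given for the primary test, is the reference and 0.001 to 0.10 is the range. The control group at the look is not stated either, so both 10 v 10 and 10 v 25 are shown. Data are normal on the analysis scale, tests are pooled two-sample t-tests, matching is ignored, and the groups are taken as comparable.

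**Step 1: reproduce the sample size.** With a standardised difference d = 0.5/0.5 = 1.0, the normal approximation gives n = 2(1.96 + 0.84)²/1.0² = 15.7, so 16 per group. The t-test calculation gives 16.7, so 17 per group (power 0.807; 16 per group gives 0.781). The stated 17 is therefore a single-test figure with no allowance for a look. Read on the log scale, a 50% reduction is d = ln 2/0.5 = 1.39. Both effects are carried forward.

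**Step 2: type I error with a 0.05 look.** The error is 1 − P(|Z₁| < 1.96 and |Z₂| < 1.96), where the correlation of Z₁ and Z₂ is the square root of the information fraction.

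- 10 v 10, then 25 v 25: fraction 10/25 = 0.40, correlation 0.632, error 0.086. Simulated t-tests give 0.0868.
- 10 v 25, then 25 v 25: fraction [1/(1/10 + 1/25)]/(25/2) = 7.14/12.5 = 0.57, correlation 0.756, error 0.081. Simulated t-tests give 0.0808.

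**Step 3: other look levels, final test at 0.05 (2,000,000 simulated null trials).**

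| Look level | 10 v 10 | 10 v 25 |
|---|---|---|
| 0.10 | 12.9% | 12.2% |
| 0.05 | 8.7% | 8.1% |
| 0.01 | 5.6% | 5.4% |
| 0.001 | 5.0% | 5.0% |

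**Step 4: stopping at a 0.05 look (1,000,000 simulated trials per effect).**

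| True effect, look | Chance of stopping | Mean estimate if stopped | Overstatement |
|---|---|---|---|
| 1.0 SD, 10 v 10 | 56% | 1.30 | 30% |
| 1.0 SD, 10 v 25 | 74% | 1.16 | 16% |
| 1.39 SD, 10 v 10 | 83% | 1.51 | 9% |
| 1.39 SD, 10 v 25 | 95% | 1.43 | 3% |

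An early stop is thus more likely than not under either planning effect.

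**Step 5: levels that restore 5%.** Two-sided 0.001 at the look with 0.0496 at the end gives overall error 0.0498 (10 v 10) or 0.0496 (10 v 25). A look at 0.0019 with 0.0492 at the end gives 0.0500 or 0.0495. Power at 1.0 SD is 93.4% for the single 25 v 25 test and 93.3% under either pair.

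**The case against.** The strongest reply is that interim outcomes, levels and alpha allocation usually belong in an SAP, and no SAP was available here. That would answer a complaint of missing detail. It does not answer this one: the protocol itself commits to stopping and concluding the study, refers to no other document for the criterion, and gives the primary test the full 0.05.

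A second reply is that the word significant may be meant clinically, as it is elsewhere in section XI, and so could cover harm or futility. That reading is possible. But the look covers outcomes as well as safety, and maximal 24-hour VIS would be known a day after each implant. Under either reading the study can be concluded with no criterion.

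Several limits on the size do stand:

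- The inflation is conditional on VIS being tested and on the level used.
- It is two-sided. The chance of falsely claiming benefit is half of it, about 4.3% or 4.0%, against 2.5% for a single test.
- Controls are matched to enrolled patients, so 10 v 10 is the more natural reading; 10 v 25 is the other end of the range.
- Section VIII also says that mean and cumulative VIS will be compared as the primary outcome, so the single test is less clean than its hypothesis statement suggests.
- Confounding from historical controls may matter more than a few points of type I error, and no alpha rule corrects it.

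**Conclusion.** The concern holds and should be fixed. What is certain is the text: a look with a safety purpose can conclude the study on undefined significance, and the primary test is stated and sized as one two-sided 0.05 test with nothing held back.

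The size is illustrative. If the look tests maximal 24-hour VIS at 0.05, the overall error is 8.7% or 8.1%, which is 1.7 or 1.6 times the stated rate. A look at 0.001 leaves it at about 5.0%. A look that does not test VIS leaves it at 5%, but the stopping decision would still have no criterion.

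**What to change.** Choose one.

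**(a) Simplest.** Make the 10-subject look safety-only, with no between-group test of VIS or any other efficacy outcome, and delete the stop-for-significance sentence in section XI. The final test stays at 0.05. The cost is the option of stopping early for efficacy, so up to 25 − 10 = 15 more treated subjects are enrolled. There is no bias from early stopping.

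**(b) Keep the stop.** Name mean maximal 24-hour VIS as the tested outcome in section XI, set two-sided p<0.001 at the look, and change the final level in section VIII to 0.0496 (or use 0.0019 with 0.0492). Power is essentially unchanged, but early stops become rarer and, when they occur, overstate the effect more than at a 0.05 look:

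| True effect, look | Chance of stopping: 0.05 look → 0.001 (0.0019) | Overstatement if stopped: 0.05 look → 0.001 (0.0019) |
|---|---|---|
| 1.0 SD, 10 v 10 | 56% → 8.5% (12%) | 30% → 70% (64%) |
| 1.0 SD, 10 v 25 | 74% → 20% (27%) | 16% → 48% (43%) |
| 1.39 SD, 10 v 10 | 83% → 26% (34%) | 9% → 34% (30%) |
| 1.39 SD, 10 v 25 | 95% → 54% (63%) | 3% → 18% (15%) |

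Averaged over stopped and completed studies, bias is 1–10% with a 0.05 look and 4–5% with 0.001. Option (b) therefore protects the error rate but does not reliably reduce bias.

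The final levels in (b) assume a 25 v 25 final test. If the sample size is revisited at this look under either option, base the change on design assumptions such as the SD and the attrition/cross-over rate, not on the observed group difference.

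The edit is two sentences in section XI and, for (b), one number in section VIII.
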